1.2. Study Objectives

1.2.1. Primary Objectives

The primary objective of the study is to describe the safety and tolerability of fasinumab, including Adverse events of special interest (AESIs), in patients with pain due to radiographically-confirmed OA of the knee or hip.

1.2.2. Exploratory Objectives

Other objectives of the study are:

- To assess the use of paracetamol/acetaminophen for the fasinumab arms compared to placebo from baseline to week 16
- To assess the use of paracetamol/acetaminophen for the fasinumab arms compared to placebo from baseline to week 52
- To assess the use of standard-of-care analgesic medication, including NSAIDs, for non-OA pain in patients randomized to fasinumab compared to placebo from week 16 through the end of treatment
- To assess time to JR

1.2.3. Additional Objectives for the Efficacy sub-study

The objective of the sub-study is to evaluate the efficacy of fasinumab compared with placebo when administered to patients with pain due to radiographically-confirmed OA of the knee or hip.

1.2.4. Modifications from the Statistical Section in the Final Protocol

The following exploratory endpoint is in the protocol but will not be included in the analysis plan since there is no definitive literature or guideline on the criteria for needing joint replacement:

- Incidence of and time to cases meeting pre-specified criteria for needing joint replacement.

The following exploratory endpoints are not listed in the protocol but are included in the analysis plan:

- Time to Adjudicated Arthropathy (AA), time to Destructive Arthropathy (DA)

The following lab safety endpoint is not listed in the protocol but is included in the analysis plan:

- High-sensitivity C-reactive protein (hs-CRP)

1.2.5. Revision History for SAP Amendments

The language of Section 7 “Timing of Statistical Analysis” was updated to clarify that the week 72 analysis is not the final analyses. Section 8 “Interim Analyses” was updated to clarify when interim analyses may be performed.

2. INVESTIGATION PLAN

2.1. Study Design and Randomization

This is a Phase 3, randomized, double-blind, multi-dose, placebo-controlled study to evaluate the long-term safety and efficacy of fasinumab in patients with pain due to osteoarthritis of the knee or hip. Patients are randomized into either the main study or the efficacy sub-study. After the 16-week sub-study, efficacy sub-study patients continue on the randomized treatment as part of the Long-Term Safety (LTS) study in which dosing will continue through week 48. The LTS study is made up of both main study patients and efficacy sub-study patients.

There have been several modifications to the randomization scheme for both the main study and the efficacy sub-study as follows:

- Original Protocol, Amendment 1 & 2

Under the original protocol and amendments 1 and 2, main study patients were randomized to 6 mg or 9 mg Q4W or matching placebo in a 2:2:1 ratio. Efficacy sub-study patients were to be randomized to 6 mg or 9 mg Q4W or matching placebo in a 1:1:1 ratio. Patients randomized to these earlier versions of the protocol with the 6 mg or 9 mg Q4W dosing regimen or matching placebo were discontinued from study medication but encouraged to otherwise continue all protocol visits and complete all study procedures with the exception of receiving study medication. Efficacy sub-study enrollment did not start under the original protocol and amendment 1 and 2.

- Amendment 3 & 4

Under amendment 3 and 4, main study patients were randomized to 6 mg Q8W or matching placebo in a 2:1 ratio. Efficacy sub-study patients were to be randomized to 6 mg Q8W or matching placebo in a 1:1 ratio. However, there were patients enrolled into the efficacy sub-study under amendment 3 and 4.

- Amendment 5 and 6

Under amendment 5 global or later, main study patients were to be randomized to 6mg fasinumab Q8W, 3 mg fasinumab Q4W, 1 mg Fasinumab Q4W, or matching placebo Q4W in a 1:2:2:1 ratio. However, there were no patients enrolled into the main safety study under amendment 5 or amendment 6. Efficacy sub-study patients were randomized to 6 mg fasinumab Q8W, 3 mg fasinumab Q4W, 1 mg fasinumab Q4W, 1 mg fasinumab Q8W, or matching placebo Q4W in a 1:1:1:1:1 ratio. Efficacy sub-study has completed enrollment as of 7 February 2018.

Due to the recommendation of the Independent Data Monitoring Committee, the 3mg Q4W and 6mg Q8W doses have been discontinued as described above. This SAP will apply to the amended protocol reflecting the most recent change in doses recommended by the IDMC, now including only the 1 mg Q4W and 1mg Q8W doses and placebo arms.

- Amendment 7 (urgent safety measure)

Issued on 24 May 2018, all patients previously randomized to 3 mg Q4W or 6 mg Q8W under earlier versions of the protocol will be discontinued from study drug but encouraged to otherwise complete all remaining study visits and study procedures in the follow-up period, and the end of study phone call. Anyone previously randomized to 9 mg Q4W or 6 mg Q4W (or matching placebo) before amendment 3, or randomized to 6 mg Q8W or 3 mg Q4W under amendment 3 or subsequent amendments, was discontinued from study drug and encouraged to complete all remaining study visits and study procedures in the follow up period and the end of study phone call.

- Amendment 8

Under amendment 8, patients will be enrolled into the main safety study. They will be randomized in a 3:3:1 ratio of fasinumab 1 mg Q8W, 1 mg Q4W or placebo. Patients randomized to 1 mg Q8W will receive alternating placebo injections at the monthly visits where active study medication drug will not be given to maintain the blind.

Stratification for the main study and the efficacy sub-study are as follows:

Main study stratification

- Randomization is stratified by screening K-L score (2-3, 4) and by geographic region (North America, Latin America, Europe, or Asia/Pacific/South Africa).

Efficacy sub-study stratification

- Randomization is stratified by screening K-L score (2-3, 4), geographic region (North America, Latin America, Europe, or Asia/Pacific), and by index joint.

2.2. Sample Size and Power Considerations

Long Term Safety study

The sample size for this long-term safety study was selected according to regulatory requirements for sufficient patients with adequate treatment exposure. With approximately 1750 patients expected to be treated with placebo, a total of up to 7000 patients was planned to be randomized. This study will provide an adequate assessment of safety in patients with pain associated with OA. For example, based on Exact Binomial Testing, with approximately 5250 patients with pain

associated with OA exposed to fasinumab, if the observed incidence rate of is 1.0%, one can be 97.5% confident that the true incidence rate is not greater than 1.3% (Table 1).

Departures from planned sample sizes will be described in the CSR.

Table 1: Observed Incidence Rate (n/N) and 95% CI (Based on Exact Binomial Test) (%)

	2-sided 95% CI
Observed Incidence Rate	All fasinumab combined (N=5250)
0.5%	(0.32%, 0.72%)
1%	(0.74%, 1.30%)
2%	(1.64%, 2.42%)
3%	(2.56%, 3.51%)
4%	(3.49%, 4.57%)
5%	(4.42%, 5.61%)

Efficacy Sub-study

The sample size of the efficacy sub-study was selected to have a sufficient number of patients to allow treatment comparisons of primary efficacy endpoints. The effect size for WOMAC pain subscale score, WOMAC physical function subscale score and Patient Global Assessment were 0.46, 0.46, and 0.36, respectively, as observed in the phase 2 study R475-PN-1227. To maintain the overall significance level of 0.05, the sequential multiple test procedure as described in Section 5.6.1 is applied to the hypothesis tests for the primary and secondary endpoints.

Assuming a dropout rate of 15% at week 16, with 200 patients per treatment arm, there will be at least 96% power to detect an effect size of 0.46 for WOMAC pain and physical function subscale scores based on a 2-sided test at the 0.0167 significance level. This sample size will provide at least 82% power to detect an effect size of 0.36 for Patient Global Assessment score.

[figure not shown]

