**Statistical Plan**

This study will contribute to the overall assessment of fasinumab safety in patients with pain associated with OA.

Treatment-emergent adverse events (TEAEs) and treatment-emergent AESIs will be listed and summarized by treatment group. Differences in event rate for AESIs between fasinumab and placebo will be estimated using exact binomial confidence intervals.

The sample size of the efficacy sub-study was selected to have a sufficient number of patients to allow treatment comparisons of sub-study primary efficacy endpoints. The effect size for WOMAC pain subscale score, WOMAC physical function subscale score and Patient Global Assessment were 0.46, 0.46, and 0.36, respectively as observed in the phase 2 study R475-PN-1227. Assuming a dropout rate of 15% at week 16, 200 patients per treatment arm, would provide at least 96% power to detect an effect size of 0.46 for WOMAC pain and physical function subscale scores based on a 2-sided test at the 0.0167 significance level. The sample size will provide at least 82% power to detect an effect size of 0.36 in Patient Global Assessment score.

The primary efficacy variables will be analyzed using a multiple imputation approach with mixed-effect model for repeated measure (MMRM) based on the FAS with adjustment for missing data due to treatment discontinuation for the reasons of lack of efficacy or AEs assuming the WOMAC scores would on average return to baseline values. The missing data for patients who discontinued treatment due to lack of efficacy or AEs will be imputed with values centered at the mean baseline value of the treatment group that patients were randomized to. Data collected after discontinuing treatment up to week 16 will not be used in the primary efficacy analysis, but used in a treatment policy sensitivity analysis. Sensitivity analysis using tipping point approach with multiple imputation will also be performed to assess the robustness of the results due to treatment discontinuation.

For analysis of continuous variables in secondary endpoints, the analysis method is the same as for the primary variables. For analysis of categorical variables in secondary endpoints (if identified later), the Cochran-Mantel-Haenszel approach stratified by the randomization strata will be used.

---

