### 1.3.2. Rationale for Dose Selection

Previous versions of this protocol randomized patients to receive fixed-dose, subcutaneous (SC) injections of fasinumab at 6 mg Q8W (amendment 3 onwards in the main study) and 1 mg Q8W, 1 mg Q4W, 3 mg Q4W, 6 mg Q8W (amendment 5 in the efficacy sub-study), or matching placebo. The purpose of the 1 mg Q8W dose regimen is to aid in the determination of a minimally effective dose. An independent DMC recommended discontinuing 6 mg Q8W and 3 mg Q4W (expected to have similar exposure to 6 mg Q8W) following a review of unblinded data from this ongoing study. The recommendation was based on an imbalance in clinically relevant adverse events including time to total joint replacement, peripheral edema, arthralgia and a trend towards early fractures in patients administered 6 mg Q4W (dose discontinued in amendment 3, issued on 20 June 2016) or 6 mg Q8W. Based on the independent DMC review, study of lower dose levels (eg, 1 mg Q4W) may continue to be evaluated in this population. Under amendment 7, issued on 24 May 2018, all patients previously randomized to 3 mg Q4W or 6 mg Q8W under earlier versions of the protocol were discontinued from study drug but encouraged to complete all remaining study visits and study procedures in the follow-up period, and the end of study phone call. Given the discontinuation of the 3 mg and 6 mg doses, greater exposure to the fasinumab 1 mg dose is required to increase the size of the fasinumab safety database for potentially clinically relevant doses. Under amendment 8, issued on 11 Jul 2018, patients will be in a 3:3:1 ratio to fasinumab 1 mg Q8W, 1 mg Q4W or placebo. This randomization ratio was chosen based on the need to enroll more patients on the 1 mg dose regimens and the need to include placebo patients for blinding purposes.

Patients originally randomized to 6 mg Q4W or 9 mg Q4W were transitioned to 6 mg Q8W in amendment 3 (issued on 20 June 2016). These patients and patients on matching placebo were subsequently discontinued from study drug in amendment R475-PN-1523.04EU (issued on 12 January 2017) and amendment 5 global (issued on 16 March 2017), but encouraged to otherwise continue all protocol visits and complete all study procedures with the exception of receiving study drug. This decision was based on data from the phase 2/3 study, R475-PN-1227, which showed an increase in AA events that occurred more frequently at the highest doses evaluated (6 mg and 9 mg Q4W).

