### 9.1. Statistical Hypothesis for the Sub-Study Population

The primary treatment comparison for the WOMAC pain and physical function subscale scores is declared superior only if the comparisons are significant for both WOMAC pain and physical function subscale scores. Hence, there are 6 hypotheses to be tested between the primary and key secondary efficacy endpoints. A hierarchical testing procedure will be used to control the overall type I error rate at 0.05 for the 2 co-primary endpoints and the secondary endpoints across the 2 dose regimens. The hierarchical testing order will be detailed in the SAP. The hypotheses to be tested are:

- H11: There is no treatment difference between fasinumab 1 mg Q4W and placebo in WOMAC pain or physical function subscale scores at week 16 versus there is treatment difference in WOMAC pain and physical function subscale scores at week 16
- H12: There is no treatment difference between fasinumab 1 mg Q4W and placebo in Patient Global Assessment score at week 16 versus there is treatment difference in Patient Global Assessment score at week 16
- H13: There is no treatment difference between fasinumab 1 mg Q4W and placebo in the proportion of patients with  $\geq 30\%$  improvement in the WOMAC pain subscale scores at week 16 versus there is treatment difference in proportion of patients with  $\geq 30\%$  improvement in WOMAC pain at week 16
- H21: There is no treatment difference between fasinumab 1 mg Q8W and placebo in WOMAC pain or physical function subscale scores at week 16 versus there is treatment difference in WOMAC pain and physical function subscale scores at week 16
- H22: There is no treatment difference between fasinumab 1 mg Q8W and placebo in Patient Global Assessment score at week 16 versus there is treatment difference in Patient Global Assessment score at week 16
- H23: There is no treatment difference between fasinumab 1 mg Q8W and placebo in the proportion of patients with  $\geq 30\%$  improvement in the WOMAC pain subscale scores at week 16 versus there is treatment difference in proportion of patients with  $\geq 30\%$  improvement in WOMAC pain at week 16

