**Table 6: Observed Incidence Rate (n/N) and 95% CI (Based on Exact Binomial Test) (%)**

	2-sided 95% CI
Observed Incidence Rate	All fasinumab combined (N=5250)
0.5%	(0.32%, 0.72%)
1%	(0.74%, 1.30%)
2%	(1.64%, 2.42%)
3%	(2.56%, 3.51%)
4%	(3.49%, 4.57%)
5%	(4.42%, 5.61%)

The sample size of the efficacy sub-study has been selected to have a sufficient number of patients to allow treatment comparisons of primary efficacy endpoints. The effect size for WOMAC pain subscale score, WOMAC physical function subscale score and Patient Global Assessment were 0.46, 0.46, and 0.36, respectively, as observed in the phase 2 study R475-PN-1227. Assuming a dropout rate of 15% at week 16, with 200 patients per treatment arm, there will be at least 96% power to detect an effect size of 0.46 for WOMAC pain and physical function subscale scores based on a 2-sided test at the 0.0167 significance level. This sample size will provide at least 82% power to detect an effect size of 0.36 for Patient Global Assessment score.

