5.2.7. Analysis of Efficacy Data

5.2.7.1. Analysis of Primary Efficacy Variable(s)

5.2.7.1.1. Primary Efficacy Analysis

The co-primary efficacy endpoints in the efficacy sub-study are:

- Change from baseline to week 16 in the WOMAC pain subscale score
- Change from baseline to week 16 in the WOMAC physical function subscale score

The primary treatment comparison for the WOMAC pain subscale score as well as the WOMAC physical function subscale score is declared superior only if the comparisons are significant for both WOMAC pain and physical function subscale scores at any of the allowed doses. Hence there are 6 hypotheses to be tested between the primary and key secondary endpoints. A hierarchical procedure will be used to control the overall Type-1 error rate at 0.05 for the 2 co-primary endpoints and the secondary endpoints across the 2 dose regimens. Each hypothesis will be formally tested only if the preceding one is significant at the 2-sided 0.05 significance level. The hierarchical testing order for the 6 hypothesis is as follows:

- H_{11} : There is no treatment difference between fasinumab 1 mg Q4W and placebo in WOMAC pain or physical function subscale scores at week 16 versus there is a treatment difference in WOMAC pain and physical function subscale scores at week 16
- H_{12} : There is no treatment difference between fasinumab 1 mg Q4W and placebo in Patient Global Assessment score at week 16 versus there is a treatment difference in Patient Global Assessment score at week 16
- H_{13} : There is no treatment difference between fasinumab 1 mg Q4W and placebo in the proportion of patients with $\geq 30\%$ improvement in the WOMAC pain subscale scores at week 16 versus there is a treatment difference in proportion of patients with $\geq 30\%$ improvement in WOMAC pain at week 16
- H_{21} : There is no treatment difference between fasinumab 1 mg Q8W and placebo in WOMAC pain or physical function subscale scores at week 16 versus there is a treatment difference in WOMAC pain and physical function subscale scores at week 16

- H₂₂: There is no treatment difference between fasinumab 1 mg Q8W and placebo in Patient Global Assessment score at week 16 versus there is a treatment difference in Patient Global Assessment score at week 16

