Each imputed data set will be analyzed using the MMRM model with treatment, randomization strata, and relevant baseline included in the model. For each δ the SAS MIANALYZE procedure will be used to generate valid statistical inferences by combining results from the 50 analyses using Rubin's formula. By progressively increasing δ , the sensitivity analysis will explore the tipping points, e.g., δ value when the p-value for a treatment comparison is above 0.0167, 0.0333 or 0.05. Results will be then summarized using summary tables and graphs.

Per Protocol Set Analysis

Sensitivity analyses based on the PPS will be performed using the MMRM approach.

Subgroup Analysis

Descriptive analyses will be performed on the primary endpoints and key secondary endpoint of PGA to summarize the treatment effects across subpopulations defined by baseline randomization strata (index joint and K-L score category), demographics (age group, sex, race) and baseline characteristics (weight and BMI categories). Subgroup analysis based on other medical conditions may also be performed. Forest plots for the subgroup analysis will be provided.

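### Sub-study power is stated at two-sided 0.0167, a level no planned test uses; under the planned 0.05 fixed sequence, power for the 1 mg Q8W co-primary test is capped at about 91%, not 96%

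*SAP*

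**What the plan says.** **Power statement.** SAP 2.2 takes standardised effects of 0.46 (WOMAC pain), 0.46 (WOMAC physical function) and 0.36 (PGA) from the phase 2 study, with 200 patients per arm and 15% dropout at week 16. It claims at least 96% power for "WOMAC pain and physical function subscale scores based on a 2-sided test at the 0.0167 significance level" and at least 82% for PGA. Protocol 9.2 repeats this ("there will be at least 96% power to detect an effect size of 0.46 for WOMAC pain and physical function subscale scores"), as does the synopsis ("200 patients per treatment arm, would provide at least 96% power to detect an effect size of 0.46"). No regimen is named, and the figures are not described as per comparison.

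**Testing procedure.** Protocol 9.1: "A hierarchical testing procedure will be used to control the overall type I error rate at 0.05". SAP 5.2.7.1.1 lists H11, H12 and H13 (1 mg Q4W: both WOMAC co-primaries, PGA, 30% WOMAC pain responders), then H21, H22 and H23 (the same for 1 mg Q8W). "Each hypothesis will be formally tested only if the preceding one is significant at the 2-sided 0.05 significance level". H11 and H21 each require both co-primaries to be significant.

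**Related text.** Just before its power figures, SAP 2.2 says that "the sequential multiple test procedure as described in Section 5.6.1 is applied to the hypothesis tests for the primary and secondary endpoints". Section 5 of the SAP contains only 5.1 and 5.2, so there is no Section 5.6.1. The SAP tipping-point rule (5.2.7.1.2) gives as examples the point at which "the p-value for a treatment comparison is above 0.0167, 0.0333 or 0.05". The matching rule in Protocol 9.5.2.1 uses 0.05 alone.

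**The concern.** The power statement and the test procedure use different significance levels. The stated 0.0167 equals 0.05/3 to four decimals, which suggests a remnant of a split-alpha scheme, though the documents do not say so. A fixed sequence at full alpha behaves differently from a split. The early hypotheses gain power. The late ones lose it, because each must wait for every hypothesis before it.

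The loss falls on 1 mg Q8W. Protocol 1.3.2 says of it: "The purpose of the 1 mg Q8W dose regimen is to aid in the determination of a minimally effective dose". SAP 2.2 names no regimen, so a reader would naturally take 96% as the chance of a positive co-primary result for either one. If 1 mg Q4W misses on PGA or on the responder endpoint, H21 is never formally tested. The missing claim for 1 mg Q8W could then be misread as lack of effect in a well-powered comparison.

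**Working it through.** **Inputs (SAP 2.2 and 5.2.7.1.1).** Evaluable n = 200 × 0.85 = 170 per arm; d = 0.46 for each WOMAC score and 0.36 for PGA; equal allocation; two-sided tests.

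**Formula.** Noncentrality = d√(n/2), on 2n − 2 degrees of freedom. By normal approximation, power = Φ(d√(n/2) − z), where z is the two-sided critical value. With n = 170, √85 = 9.22, so the noncentrality is 4.241 for WOMAC and 3.319 for PGA.

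**1. Reproduce the plan's figures, then change only alpha.**

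| Test | Alpha | Normal approximation | Noncentral t |
|---|---|---|---|
| WOMAC, d = 0.46 | 0.0167 (z = 2.393) | Φ(1.848) = 96.8% | 96.6% |
| PGA, d = 0.36 | 0.0167 | Φ(0.926) = 82.3% | 81.9% |
| WOMAC, d = 0.46 | 0.05 (z = 1.960) | Φ(2.281) = 98.9% | 98.8% |
| PGA, d = 0.36 | 0.05 | Φ(1.359) = 91.3% | 91.1% |

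The stated 96% and 82% are therefore single-endpoint, single-comparison figures at 0.0167.

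**2. The 1 mg Q4W steps.** Bivariate normal power for both co-primaries at 0.05 is 97.8%, 97.9% and 98.2% at endpoint correlations of 0, 0.5 and 0.8. Cumulative power through H12 is 89.3%, 90.2% and 91.0%. Both beat the stated floors of 96% and 82%.

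**3. A ceiling for H21.** Rejecting H21 requires rejecting H12, and rejecting H12 requires a significant PGA result for 1 mg Q4W. Hence:

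P(reject H21) ≤ P(1 mg Q4W PGA significant at 0.05) = 91.1%.

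This needs no correlation, no responder rate and no assumption about the 1 mg Q8W effect. If all 200 per arm were fully informative, noncentrality is 0.36 × √100 = 3.6 and the ceiling is 94.9%. The PGA gate alone reaches 96% only with 214 informative patients per arm (213 by normal approximation), more than the 200 planned.

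**4. The full chain.** Simulation with normal test statistics, 1,000,000 draws per case, n = 170, the same effects in both regimens, and between-dose correlation 0.5 because placebo is shared. The documents give no responder rates, so the power of H13 is an assumption.

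| Assumed H13 power | H21 at endpoint correlation 0 / 0.5 / 0.8 |
|---|---|
| Always passes | 87.5% / 88.8% / 89.9% |
| 95% | 83.1% / 85.8% / 88.4% |
| 90% | 78.8% / 82.3% / 85.4% |
| 80% | 70.0% / 74.4% / 77.7% |

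With 200 informative per arm and H13 always passing, H21 is 93.5%, 93.9% and 94.4%, still below 96%. H22 is 82–85% if H13 always passes and 74–81% if H13 has 90% power. Since 82% lies within what is possible, no shortfall is claimed for H22.

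**The case against.** The strongest reply is that nothing stated is false as a marginal claim. The arithmetic at 0.0167 is right, and at 0.05 every single comparison has more power than stated, so both floors hold test by test. The documents never promise cumulative power for H21, and the order and gating are set out openly. The text also records how n was chosen. SAP 2.1 says sub-study enrolment was complete by 7 February 2018, so restating power cannot change n, alpha or any analysis. The SAP will in any case report the difference from placebo with its 95% confidence interval, so an untested H21 does not hide the 1 mg Q8W estimate.

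Much of this stands. The mismatch is conservative for 1 mg Q4W, and type I error control is unaffected. The H13 scenarios are illustrative. Their low ends use zero endpoint correlation, which is implausible because H13 dichotomises the same WOMAC pain score used in H11. Counting dropouts as uninformative is also a simplification, because the analysis imputes for all randomised patients.

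It does not rescue the statement. SAP 2.2 places the power figures directly after a sentence saying that the sequential procedure is applied to maintain the overall 0.05, so they read as power under that procedure. The ceiling on H21 uses only the plan's own inputs and stays below 96% even with no dropout.

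**Conclusion.** The concern holds. The stated power rests on a significance level that none of the six hypotheses uses. For 1 mg Q4W the correct figures are better than stated. For the 1 mg Q8W co-primary test, power in the planned sequence is at most 91.1%, or 94.9% if all 200 per arm are informative, against the 96% a reader would infer. It is 87.5–89.9% if the responder test always passes, and lower by an unstated amount otherwise.

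The ceiling depends only on the plan's n, dropout and PGA effect size. The chain figures also assume equal effects in both regimens, endpoint correlation of 0 to 0.8 and between-dose correlation of 0.5. The effect of return-to-baseline imputation on power was not modelled. This should be corrected, but it does not threaten the validity of the tests. The wrong cross-reference and the leftover tipping-point thresholds are secondary.

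**What to change.** In SAP 2.2, Protocol 9.2 and the synopsis, replace the 0.0167 statement with power for each step of the sequence in SAP 5.2.7.1.1 at two-sided 0.05. For example:

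> With 200 patients randomised and 170 evaluable per arm, power is about 98% for H11 (both co-primaries) and about 89–91% for H11 and H12 together. H21 is tested only if H11, H12 and H13 are all significant. Cumulative power for H21, H22 and H23 is [sponsor's figures], assuming [responder rates] and [endpoint correlations].

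The sponsor should supply its own responder-rate and correlation assumptions. If 96% and 82% are kept as the historical basis for n, label them as per-comparison figures at a level no longer used.

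Also change the SAP 2.2 cross-reference from Section 5.6.1 to 5.2.7.1.1, and use 0.05 alone in the tipping-point rule of SAP 5.2.7.1.2, in line with Protocol 9.5.2.1.

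The change is to text only; enrolment, test order and analyses stay as they are. The cost is a less favourable stated power for 1 mg Q8W, and a commitment by the sponsor to assumptions it has not yet written down.
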